## 7.5 Study events table

Procedure	Pre-Treatment Evaluations	Treatment Period	End of Therapy	Follow-Up
	(within 30 days before first dose of treatment)	(within 5 days before second and third dose of treatment)	(day of surgery, preferably, or within 2 days before surgery)	(within 30 days after surgery)
Eligibility Assessments				
Informed Consent	X 			
Inclusion/Exclusion Criteria	X			
Medical History and Physical Examination	X			
Pregnancy Test	X			
Safety Assessments				
Medical History and Physical Examination 		X		X 
Vital Signs (blood pressure, heart rate, temperature)	X	X	X	X 
Toxicity Assessments/Adverse Events	X	X		X 
Laboratory Tests				
Hematology Profile	X	X	X	
Serum Chemistry Profile	X	X	X	
Imaging studies				
CT Scan or MRI of the H&N	X		X 	
Audiometry	X 			X 
Pharmacodynamic Assessments				
Tumor specimen biomarkers	X 		X	
Skeletal muscle/adipose tissue biomarkers 			X	
Blood-based biomarkers 	X	X 	X	X

 Informed consent should be obtained prior to registering for trial, undergoing protocol-specific evaluations, or receiving treatment.

 Initial medical history should include past or current medical conditions, current medications, date of diagnosis, stage (using the American Joint Committee on Cancer Staging Manual, Sixth Edition or higher), pathological confirmation of HNSCC and tentative date of surgery (if available). Any pre-existing toxicity should be documented and recorded as well. The physical examination will include an evaluation by pertinent body system, height (pretreatment only), weight, and body surface area (BSA), as well as ECOG performance status (pretreatment only) should be documented.

 26 mL of blood (optional) will be collected and stored for additional studies of interest

 May be obtained at any time-point between the last dose of the study drug(s) and the surgical procedure. However, preferably, scans will be performed the day before surgery.

 Baseline tumor tissue may be obtained more than 30 days prior to treatment initiation.

 Collection of skeletal muscle / adipose tissue is optional and will only be obtained if the patient has previously given consent and if the collection of these additional tissues is considered feasible (i.e., not associated with unreasonable risks) by the surgeon during the operative procedure.

 Blood-based biomarkers will be obtained only before the second dose of treatment.

 A telephone call to assess adverse events may substitute for a medical history, physical examination, and vital signs in the event the patient is not evaluated by the investigator or his/her designee within 30 days after surgery

 Patients randomized to receive treatment with IMC-A12 (i.e. Arm B and Arm C) are required to have an audiometric evaluation within 90 days before starting treatment with the study drug(s). For all patients who received at least 1 dose of IMC-A12, a repeat audiometric evaluation will be performed within 90 days after surgery.

## 8 Adverse events assessment

### 8.1 *Performing adverse events assessments*

The assessment of reported adverse events will be performed at least within 5 days before the second and, if applicable, third treatment course, and within 30 days after surgery. Adverse events will be classified according to the National Cancer Institute (NCI) Common Terminology Criteria for Adverse Events (CTCAE) version 3.0.

### 8.2 *Importance of adverse event reporting*

Timely and complete reporting of safety information assists in identifying any untoward medical occurrence, thereby allowing: (1) protection of safety of study patients; (2) a greater understanding of the overall safety profile of the investigational products; (3) recognition of dose-related investigational product toxicity; (4) appropriate modification of study protocols; (5) improvements in study design or procedures; and (6) adherence to worldwide regulatory requirements.

### 8.3 *Adverse events definition*

#### 8.3.1 *Adverse event*

An *Adverse Event (AE)* is defined as any new untoward medical occurrence or worsening of a pre-existing medical condition in a patient administered a medicinal product that does not necessarily have a causal relationship with this treatment. An AE can therefore be any unfavorable and unintended sign (including an abnormal laboratory

finding, for example), symptom, or disease temporally associated with the use of a medicinal (investigational or marketed) product, whether or not considered related to the medicinal (investigational or marketed) product. Planned medical interventions (e.g., planned surgical resection) will not be considered an adverse event. For the purpose of this study, adverse events that in the opinion of the treating investigator are related to planned surgical procedure (e.g., usual pain, usual bleeding, intra- or post-operative electrolyte imbalances and other clinically insignificant laboratory abnormalities) will not be captured and/or reported.

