#### **8.4 Assessment of causality**

The following categories and definitions for assessing the causal relationship of an event to the investigational product(s) are provided as a guide to be used for every event reported in Eli Lilly & Co. clinical trials:

- Definite/Certain: there is a reasonable causal relationship between the investigational product(s) and the AE; the event responds to withdrawal of the

investigational product(s) (de-challenge) and recurs with re-challenge when clinically feasible.

- Probable: there is a reasonable causal relationship between the investigational product(s) and the AE; the event responds to de-challenge; re-challenge is not required.
- Possible: there is reasonable causal relationship between the investigational product(s) and the AE; de-challenge information is lacking or unclear.
- Not Likely: There is a temporal relationship to study drug administration, but there is not a reasonable causal relationship between the study drug and the AE.
- Unrelated: there is not a temporal relationship to the investigational product(s) administration (too early, late, or the investigational product was not taken) or there is a reasonable causal relationship between another drug, concurrent disease, or circumstance and the AE.

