## **8.5 *Collection of safety information***

Pre-existing toxicities will be collected and noted on patient's medical record.

Additionally, collection of AE information will be performed from the time the patient receives the initial infusion of the study drug(s), and must continue throughout the study until 30 days after the last dose, unless specified otherwise in the protocol. This includes pre-existing conditions or symptoms that worsened during the study, or whose relationship to the investigational product changed, but does not include pre-planned hospitalizations or procedures for pre-existing conditions. In addition, the investigator should notify Eli Lilly & Co. of any SAE or outcome that may occur after this time period that he/she believes to be related to IMC-A12 and/or cetuximab. An AE report must contain the following four basic elements: (1) an identifiable patient; (2) a suspect medicinal product; (3) an identifiable reporting source; and (4) an identifiable event or outcome. All identified AEs must be recorded and described in patient's medical record. If known, the diagnosis of the underlying illness or disorder should be recorded in

addition to the presenting symptoms. The following information should be captured for all AEs: the date of the onset and resolution; the severity of the event as determined by PI or study collaborator (see definitions in NCI-CTCAE, Version 3.0); the investigator's opinion of the relationship of the event to the investigational drug/s (certainly/definitely, probably, possibly, unlikely, or not related); the treatment required for the AE; information regarding resolution/outcome; and if the AE is serious, a clear identification of the seriousness outcome.

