## **9 Treatment emergent adverse events**

Patients will be closely monitored for treatment-related adverse events, especially infusion reactions. Adverse event monitoring will occur on a continuous basis for the duration that patients are on study therapy. In addition to the planned evaluations during follow-up visits, patients will be instructed to call their physician to report any adverse events between visits.

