## **9.2 IMC-A12**

Adverse events of concern, which may or may not be associated with IMC-A12 therapy, include infusion reactions, hyperglycemia, and peri-operative complications.

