### **9.2.3 Peri-operative complications**

Cetuximab has not been studied pre-operatively in patients with HNSCC. However, preliminary reports of two studies of cetuximab in combination with chemotherapy prior to liver resection in patients with metastatic colorectal cancer did not raise post-operative toxicity concerns. IMC-A12 has never been studied in the pre-operative setting. Although there is no pre-clinical data that suggests an increased incidence of peri-operative complications with IMC-A12, patients will be closely monitored for these adverse events. In case a higher than expected incidence of peri-operative complications is seen, considerations will be given to terminating the study, or modifying the protocol, so as to increase the interval between the last dose of the study drug(s) and the surgical procedure.

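### Section 8.3.1 excludes surgery-attributed adverse events with no severity limit, so non-serious peri-operative complications can be missing from the study safety data although the protocol commits to monitoring them

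*Combined protocol and SAP*

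**What the plan says.** All references are to the combined protocol and SAP.

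- **8.3.1** first defines an adverse event broadly, "whether or not considered related to the medicinal (investigational or marketed) product". It then says that "adverse events that in the opinion of the treating investigator are related to planned surgical procedure" are not to be captured and/or reported. The bracketed examples are ordinary pain and bleeding, electrolyte imbalances during or after the operation, and laboratory changes without clinical significance.
- **8.3.2** applies the same surgical exception to reports of serious adverse events (SAEs) to the IRB. SAEs go to the IND Office whatever their attribution, unless the protocol states otherwise. Sections 8.3.2 and 8.10 also send them to the supporting company.
- **8.4** has an unrelated category, which applies among other cases where "there is a reasonable causal relationship between another drug, concurrent disease, or circumstance and the AE".
- **8.5** states: "All identified AEs must be recorded and described in patient's medical record". It also lists the details to be collected for every event, including severity and relationship to study drug. It does not mention the surgical exclusion.
- **9** states: "Adverse event monitoring will occur on a continuous basis for the duration that patients are on study therapy". Section 8.1 schedules one assessment after surgery, within 30 days.
- **9.2** lists IMC-A12 events of concern, "which may or may not be associated with IMC-A12 therapy, include infusion reactions, hyperglycemia, and peri-operative complications". Section 9.2.3 says that IMC-A12 has never been studied pre-operatively and that "patients will be closely monitored for these adverse events". It continues: "In case a higher than expected incidence of peri-operative complications is seen", consideration will be given to terminating or modifying the study.
- **2.2** makes safety, with emphasis on the pre-operative setting, a secondary objective. **12.2.4** reports toxicity by arm on the basis of section 8.

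**The concern.** A complication after an operation is the kind of event most easily put down to the operation. The only test in 8.3.1 is the treating investigator's opinion, and that investigator knows the treatment arm. An event judged surgical therefore need not enter the study data at all, so nobody can later compare its frequency between arms or revisit the attribution.

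The events open to exclusion are of the type that 9.2.3 says will be watched. If they are filtered out before analysis, the safety tables may give an incomplete picture of peri-operative risk for a drug with no earlier pre-operative experience.

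**Working it through.** The plan states no figure on this point, so the check is mainly a comparison of texts.

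**1. Scope of the exclusion.** The criterion in 8.3.1 is opinion of relatedness to planned surgery. No grade or seriousness limit is attached. The examples are mild, but they illustrate the rule and do not bound it. A non-serious grade 3 complication attributed to surgery falls within the wording.

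**2. Does the exclusion reach the analysis?** Section 12.2.4 takes toxicity as determined in section 8, and 8.3.1 is part of section 8. The by-arm tables can therefore inherit the exclusion.

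**3. Do other routes restore the events?**
- *Medical record:* 8.5 keeps identified events there. That does not put them in the study data. Section 6.2 shows that the protocol separates the two: concurrent medications go in the record but not the case report form. The conflict between 8.3.1 and 8.5 is partial, because the sentence about the record can coexist with 8.3.1, while the list of details to be collected for all events cannot easily do so.
- *SAE reporting:* the IND Office and the supporting company still receive serious events. The IRB, which section 10.3 allows to discontinue the study for safety, is subject to the surgical exception. Non-serious events have no such route.
- *Post-operative assessment:* the contact within 30 days after surgery is where most of these events would be found, and the exclusion applies to it.

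**4. Overlap with a known drug effect.** Electrolyte imbalance is one of the excluded examples. Section 9.1 lists hypomagnesemia among cetuximab adverse events. Section 9.1.5 reports it in about half of cetuximab-treated patients in other trials, severe in 10-15%, with onset from days to months. Those rates may not carry over to two or three doses, but the overlap is plain. Section 8.9 would document a laboratory abnormality that needs treatment; 8.3.1 can exclude the same abnormality if it is attributed to surgery.

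**5. Small-sample sensitivity (illustration only).** Inputs: 20 patients per arm (12.4) and 40 given IMC-A12 (arms B and C, 20 + 20). One patient is 1/20 = 5 percentage points, or 1/40 = 2.5. The upper limits below are exact (Clopper-Pearson) two-sided 95% limits; for zero events the limit is 1 − 0.025^(1/n).

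| True count | n = 20 | n = 40 |
|---|---|---|
| 0 | 16.8% | 8.8% |
| 1 | 24.9% | 13.2% |
| 2 | 31.7% | 16.9% |

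If a table shows 0/20 because one affected patient was excluded, the reader sees a limit of 16.8% where the full data would give 24.9%. This shows how sensitive a table of this size is to one patient. It does not measure how often 8.3.1 removes one.

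**6. Collection window (wording only).** Sections 8.3.2 and 8.5 run to 30 days after the last dose; 7.4 and 8.1 place the assessment within 30 days after surgery. Collection ends on post-operative day 30 − d, where d is the number of days from last dose to surgery: day 28 for d = 2, day 25 for d = 5, and day 20 at the 10-day evaluability limit. Section 8.5 allows exceptions, and the contact may fall earlier than day 30.

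**The case against.** The strongest reply is that 8.3.1 was meant narrowly. Every example is usual or trivial, and 9.2 and 9.2.3 deal with complications specifically. Read together, 8.3.1 drops expected surgical effects and 9.2.3 governs complications. Intent probably was narrow, and that stands. But the text of 8.3.1 does not say so, and 9.2.3 sets up no separate data collection.

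Second, many important complications would be serious, for example through prolonged hospitalization, and would be reported. That also stands, and it limits the point to non-serious events.

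Third, follow-up is wider than one contact. Patients attend regular surgical clinic visits and are told to call about events, unresolved drug-related toxicity is followed, and long-term toxicity is sought by chart review. These help detection but do not ensure entry in the study data.

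Fourth, a demand to record every grade 3 or higher event would collide with section 8.9, which documents laboratory abnormalities only when they meet stated criteria. This is correct, and the fix leaves 8.9 in place.

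A reader might also infer that the trial's continuation depends on the affected tables. Section 9.2.3 does not support that: it promises only consideration, sets no threshold, and does not name the tables.

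**Conclusion.** The point holds as a defect of wording with a practical consequence. Followed literally, 8.3.1 can leave non-serious peri-operative complications out of the study adverse event data and the by-arm tables, against the commitments in 2.2, 9.2 and 9.2.3. It rests on two assumptions: that sites apply 8.3.1 as written, and that the tables are built from data collected under section 8.

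The size of any loss cannot be determined, because the documents give no complication rate and no attribution rate. Three stronger conclusions are tempting but unsupported:

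- **SAEs are lost.** The IND Office and supporting-company routes remain; only the IRB route carries the surgical exception.
- **The tables are biased towards a particular arm.** Open-label attribution makes a difference between arms possible, but nothing in the documents fixes its direction.
- **The dose-limiting toxicity rule in 12.6.2 is weakened.** Its definition does not exempt surgical events, and the documents do not say whether the count would pass through the 8.3.1 exclusion. The effect is undetermined.

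The phospho-Akt primary endpoint is unaffected.

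**What to change.** Reconcile sections 8.3.1, 8.3.2, 8.5, 8.9, 9.2 and 9.2.3:

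- Limit the 8.3.1 exclusion to the usual, clinically insignificant surgical effects that its examples describe.
- Record all other peri-operative complications and all SAEs in the study adverse event data, in every arm. Laboratory abnormalities stay subject to the 8.9 criteria.
- Make attribution (surgery, cetuximab, IMC-A12) a data field and not a filter. The 8.4 scale can carry this if surgery is named.
- State in 12.2.4 that peri-operative complications are tabulated by arm regardless of attribution.
- Optionally, align the 30-day windows in 8.3.2 and 8.5 with the assessment within 30 days after surgery.

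The cost is a wording amendment and modest extra data entry for about 60 patients. No new visit or procedure is needed: the post-operative contact is already planned, and 8.5 already requires the events in the medical record.

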### **8.3.2 Serious adverse event**

#### **Serious Adverse Event Reporting (SAE) Language for M. D. Anderson-sponsored IND Protocols**

An adverse event or suspected adverse reaction is considered “serious” if, in the view of either the investigator or the sponsor, it results in any of the following outcomes:

- Death
- A life-threatening adverse drug experience – any adverse experience that places the patient, in the view of the initial reporter, at immediate risk of death from the adverse experience as it occurred. It does not include an adverse experience that, had it occurred in a more severe form, might have caused death.
- Inpatient hospitalization or prolongation of existing hospitalization
- A persistent or significant incapacity or substantial disruption of the ability to conduct normal life functions.
- A congenital anomaly/birth defect.

Important medical events that may not result in death, be life-threatening, or require hospitalization may be considered a serious adverse drug experience when, based upon appropriate medical judgment, they may jeopardize the patient or subject and may require medical or surgical intervention to prevent one of the outcomes listed in this definition. Examples of such medical events include allergic bronchospasm requiring intensive treatment in an emergency room or at home, blood dyscrasias or convulsions that do not result in inpatient hospitalization, or the development of drug dependency or drug abuse (21 CFR 312.32).

- Important medical events as defined above may also be considered serious adverse events. Any important medical event can and should be reported as an SAE if deemed appropriate by the Principal Investigator or the IND Sponsor, IND Office.
- All events except events that in the opinion of the treating physician are related to planned surgical procedure occurring during the conduct of a protocol and meeting the definition of a SAE must be reported to the IRB in accordance with the timeframes and procedures outlined in "University of Texas M. D. Anderson Cancer Center Institutional Review Board Policy on Reporting Serious Adverse Events". Unless stated otherwise in the protocol, all SAEs, expected or unexpected, must be reported to the IND Office, regardless of attribution (within 5 working days of knowledge of the event).
- **All life-threatening or fatal events**, that are unexpected, and related to the study drug, must have a written report submitted within **24 hours** (next working day) of knowledge of the event to the Safety Project Manager in the IND Office.
- The MDACC "Internal SAE Report Form for Prompt Reporting" will be used for reporting to the IND Office.
- Serious adverse events will be captured from the time the patient signs consent until 30 days after the last dose of drug. Serious adverse events must be followed until clinical recovery is complete and laboratory tests have returned to baseline, progression of the event has stabilized, or there has been acceptable resolution of the event.
- Additionally, any serious adverse events that occur after the 30 day time period that are related to the study treatment must be reported to the IND Office. This may include the development of a secondary malignancy.

#### **Reporting to FDA:**

Serious adverse events will be forwarded to FDA by the IND Sponsor (Safety Project Manager IND Office) according to 21 CFR 312.32.

**It is the responsibility of the PI and the research team to ensure serious adverse events are reported according to the Code of Federal Regulations, Good Clinical Practices, the protocol guidelines, the sponsor's guidelines, and Institutional Review Board policy.**

**SAE Investigator Communication of with Supporting Companies:**

Adverse events classified as “serious” must be recorded on the MDACC Internal Adverse Event Reporting Form and reported to the Sponsor (Safety Project Manager ORE&RM) and to Eli Lilly & Co. to comply with regulatory requirements. These SAEs will include deaths, regardless of their causal relationship to investigational product. All SAEs must be reported using the MDACC Internal Adverse Event Reporting Form. To the extent possible, the descriptive terminology and other SAE attributes entered on the MDACC Internal Adverse Event Reporting Form should approximate similar information in the patient’s medical record. Study site personnel must alert Lilly or its designee of any **serious** adverse event (SAE) within 24 hours of investigator awareness of the event via a Sponsor-approved method. Alerts issued via telephone are to be immediately followed with official notification on study-specific MDACC Internal Adverse Event Reporting Form. The completed MDACC Internal Adverse Event Reporting Form must be faxed to **Lilly’s Global Product Safety Fax Number for all SAEs at [contact] or [contact]** within 24 hours of the study site personnel’s initial notification/awareness of the event. Duly authorized study site personnel may sign completed forms; however, it is recommended that the investigator sign each final SAE report.

